8.3 Safety Variables

Adverse events and laboratory values will be graded according to the National Cancer Institute (NCI) Common Terminology Criteria for Adverse Events (CTCAE) Version 4.03.

8.3.1 Adverse Events

AEs will be coded using Medical Dictionary for Regulatory Activities (MedDRA, Version 15.1 or higher).

Baseline Signs and Symptoms

- Signs and symptoms of the patient's cancer diagnosis and/or comorbidities present on Day 1 of study drug dosing are recorded in the CRF as non-treatment emergent AEs, with actual start date, which will most often predate first dose. Baseline signs and symptoms will be reported separately from TEAEs.

Treatment-Emergent AEs (TEAEs)

- TEAEs are AEs that begin on Day 1 of study treatment or later during the on-study period. Baseline signs and symptoms that change attribution or severity during the on-study period are TEAEs. Any ongoing TEAEs that changes in attribution or severity is captured as a new AE.

Adverse Events of Special Interest (AESI)

AEs of special interest (AESI) for durvalumab based on observed safety event during durvalumab monotherapy and/or class effects for inhibitors of PD-L1 or PD-1 include:

- Colitis
- Pneumonitis
- Alanine aminotransferase (ALT)/aspartate aminotransferase (AST) increases / hepatitis / hepatotoxicity
- Neuropathy / neuromuscular toxicity (i.e., events of encephalitis, peripheral motor and sensory neuropathies, Guillain-Barré, and myasthenia gravis)
- Endocrinopathy (i.e., events of hypophysitis, adrenal insufficiency, and hyper- and hypothyroidism)
- Dermatitis
- Nephritis
- Pancreatitis (or labs suggestive of pancreatitis – increased serum lipase, increased serum amylase).

Immune-related Adverse Event (irAE)

An irAE is defined as an AE that is associated with drug exposure and is consistent with an immune-mediated mechanism of action and where there is no clear alternate aetiology.

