## **7.3 Safety Assessments**

### **7.3.1 Adverse Events**

Assessment of adverse events will include type, incidence, severity (graded by the National Cancer Institute [NCI] Common Terminology Criteria for Adverse Events [CTCAE, Version 4.03]), timing, seriousness, and relatedness to study treatment.

Signs and symptoms of the patient's cancer diagnosis and/or comorbidities present at baseline will be recorded in the CRF as AEs beginning on Day 1 of study treatment and onward throughout the study. The actual date of onset should be recorded in all cases. Ongoing AEs that change in attribution or severity should have the date of change entered as the "end date" and a new AE record should be opened with the changed details.

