### **8.2 Adverse Events**

An adverse event (AE) is any reaction, side effect or other undesirable medical event that occurs during participation in a clinical trial, regardless of treatment group or suspected causal relationship to study treatment. A treatment emergent AE (TEAE) is an AE that occurs after the first dose of any study treatment or any preexisting condition that increases in severity after the first dose of study treatment.

All observed or volunteered AEs will be recorded in source documents and reported in the CRF. The best available medical terminology should be used to describe AEs in source documents and CRFs. Terms describing the diagnosis are preferred over individual signs and symptoms of the diagnosis. If determination of the diagnosis is delayed, record signs and symptoms and add the diagnosis as an AE when available; follow all recorded AEs to resolution. Examples of AEs include but are not limited to:

- Signs or symptoms of co-morbidity, illness, or toxicity of study treatment;
- Signs or symptoms of worsening malignancy under study (disease progression assessed by measurement of malignant lesions should not be reported as an AE).
- Laboratory abnormalities (see [Section 8.2.1](#) for guidance for reporting in CRF);
- Hypersensitivity;
- Drug abuse, dependency, overdose, withdrawal or misuse;
- Signs or symptoms of drug interactions;
- Extravasation;
- Exposure during pregnancy or via breastfeeding;
- Medication error; or
- Occupational exposure.

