12.6.1 Adverse Events

A summary of TEAEs, including the number and percentage of DLTs, number and percentage of patients reporting at least one TEAE, the number and percentage of patients reporting at least one CTCAE Grade 3 or greater TEAE, the number and percentage of patients discontinuing due to a TEAE, the number and percentage of patients with at least one serious adverse event (SAE), number and percentage of patients with at least one SAE by CTCAE grade, number and percentage of patients with at least 1 moccetinostat related TEAE, number and percentage of patients with at least 1 durvalumab related TEAE, number and percentage of patients with at least 1 TEAE related to both durvalumab and moccetinostat, number and percentage of patients with at least 1 moccetinostat related SAE, number and percentage of patients with at least 1 durvalumab related SAE, number and percentage of patients with at least 1 SAE related to both durvalumab and moccetinostat, number and percentage of patients discontinuing moccetinostat due to a TEAE, number and percentage of patients discontinuing durvalumab due to a TEAE, number and percentage of patients discontinuing moccetinostat due to a TEAE related to moccetinostat, number and percentage of patients discontinuing durvalumab due to a TEAE related to durvalumab, and the number and percentage of deaths will be presented. TEAEs are those that first occur or increase in severity or relationship to study treatment after the first dose of study treatment and not more than 30 days after the last dose of study treatment. In reality, all adverse events that change in severity or relationship to study treatment are assigned a new start date and captured as a new record. All AEs will be coded according to the MedDRA Version 19.0 dictionary by SOC, PT, and severity grade using NCI CTCAE Version 4.03.

A breakdown of the number and percentage of patients reporting each adverse event categorized by SOC and PT will be presented. Note that counting will be by patient not event and patients are only counted once within each SOC or PT. Similar summaries for CTCAE Grade ≥ 3 TEAEs, moccetinostat-related TEAEs, durvalumab-related TEAEs, CTCAE Grade ≥ 3 moccetinostat-related TEAEs, and CTCAE Grade ≥ 3 durvalumab-related TEAEs will be presented.

Sponsor: Mirati Therapeutics, Inc.

Protocol no: 0103-020

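### SAP 8.3.1 makes a baseline symptom treatment-emergent when its severity changes in either direction, against protocol 8.2 and SAP 12.6.1, which require an increase

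*SAP*

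**What the plan says.** The plan defines a TEAE in three places.

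- **SAP 8.3.1** gives an onset rule, "TEAEs are AEs that begin on Day 1 of study treatment or later during the on-study period", and a rule for symptoms already present, "Baseline signs and symptoms that change attribution or severity during the on-study period are TEAEs". It adds: "Baseline signs and symptoms will be reported separately from TEAEs".
- **SAP 12.6.1**, which specifies the adverse event tables, says: "TEAEs are those that first occur or increase in severity or relationship to study treatment after the first dose of study treatment". It closes the window 30 days after the last dose.
- **Protocol 8.2** counts events arising after the first dose, and also "any preexisting condition that increases in severity after the first dose of study treatment".

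Two passages describe how the data are recorded. Under protocol 7.3.1, "Ongoing AEs that change in attribution or severity should have the date of change entered" as the end date of the existing record, and a new record is then opened. SAP 12.6.1 notes likewise that "all adverse events that change in severity or relationship to study treatment are assigned a new start date and captured as a new record".

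**The concern.** The rule in SAP 8.3.1 turns on change; the other two turn on increase. A cancer symptom that eases on treatment is a change but not an increase.

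The recording convention makes the difference matter. An easing symptom leaves a new record whose start date falls after the first dose. That record meets the baseline-symptom rule in 8.3.1 and, taken on its date alone, the onset rule as well.

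The TEAE flag feeds the overall summary, the system organ class and preferred term tables, the table of events in at least 10% of patients, and the maximum-grade table (SAP 12.6.1). Safety is a secondary endpoint. With no control arm, no comparison group would show how much of the count comes from baseline symptoms that improved.

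**Working it through.** The plan states no figure here, so the check sets the three definitions side by side. The grades are assumed for illustration.

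| Baseline symptom on treatment | SAP 8.3.1 | SAP 12.6.1 | Protocol 8.2 |
|---|---|---|---|
| Unchanged | Not a TEAE | Not a TEAE | Not a TEAE |
| Grade 2 worsens to Grade 3 | TEAE | TEAE | TEAE |
| Grade 3 improves to Grade 2 | **TEAE** | Not a TEAE | Not a TEAE |
| Grade 2 improves to Grade 1 | **TEAE** | Not a TEAE | Not a TEAE |
| Grade 1 resolves | No new record to flag | Not a TEAE | Not a TEAE |
| Same grade, attribution becomes related | TEAE | TEAE | **Not a TEAE** |

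1. *Improvement.* SAP 8.3.1 stands alone against the other two. The disputed record needs a baseline grade of at least 2 and a later grade that is lower but not zero. A Grade 1 symptom that improves by one grade has resolved: its record closes and no lower-graded record follows.

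2. *Attribution.* Both SAP sections let a change to related qualify by itself. Protocol 8.2 has no attribution criterion.

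3. *Window.* SAP 8.3.1 refers to the on-study period without defining it. SAP Appendix 4 treats a patient as on study until the End of Study page is completed. SAP 12.6.1 stops at 30 days after the last dose, while protocol 8.4.1 collects serious events for 90 days. If Appendix 4 sets the period, a serious event first arising on days 31 to 90 after the last dose is a TEAE under 8.3.1 and not under 12.6.1.

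4. *Programming.* SAP Appendix 4, which holds the programming specifications for safety variables, contains no TEAE derivation. Neither SAP section describes comparing a new record's grade with the baseline grade, and neither says which section prevails.

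5. *Size.* The share of patients who gain a TEAE in a given term only through improvement is the product of three proportions: those with a baseline symptom of Grade 2 or higher in that term; among these, those who fall to a lower non-zero grade; and among these, those with no true TEAE in the same term. The documents give none of the three.

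**The case against.** The strongest reply is that SAP 12.6.1 governs the tables and already excludes improvement, because it says increase. On that view its next sentence only describes data capture and redefines nothing. This is a fair reading of 12.6.1, and it means a miscount is not a settled outcome. It does not remove the conflict: 8.3.1 is the section that defines the variable, its rule is different, and no precedence is stated. The introduction to protocol section 9 lets the SAP modify the protocol's plans, but that cannot explain a SAP that disagrees with itself.

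Several limits on the effect also stand:

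- Patients are counted once per system organ class or preferred term, so an improvement adds nothing where the same patient has a true TEAE in that term.
- Protocol section 4 requires ECOG 0 or 1, and excludes patients whose adverse effects of prior therapy have not recovered to Grade 1 or lower, apart from alopecia and neuropathy. Both reduce the number of symptoms that could be affected.
- An improving baseline symptom can enter a table of Grade 3 or higher events only by falling from Grade 4 to Grade 3.
- Dose limiting toxicity requires a causal relation to treatment, so that primary endpoint is untouched.
- No hypothesis test uses TEAEs.

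**Conclusion.** Wrong as written. SAP 8.3.1 contradicts protocol 8.2 and SAP 12.6.1 on the direction of change, and the SAP gives two windows. Programmed as it stands, 8.3.1 would inflate any-cause TEAE incidence through baseline symptoms of Grade 2 or higher that improve without resolving. This rests on the recording convention being followed and on 8.3.1, not 12.6.1, being the rule that is coded.

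A reader might infer more, but the documents do not support it:

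- *That improving symptoms are already being counted.* This depends on which definition is programmed.
- *That the excess can be put as a percentage of patients.* Guessing that 30–50% carry a graded baseline symptom and 10–30% of these improve gives 0.30 × 0.10 = 3% to 0.50 × 0.30 = 15%. Both inputs are assumptions, and that base wrongly includes Grade 1 symptoms, which leave no lower-graded record when they improve. The size is unknown.
- *That improvement is reported as drug toxicity.* TEAEs are any-cause, and events related to each drug have separate tables.
- *That a time-to-onset result is distorted.* Timing appears in the description of the safety endpoint, but the SAP plans no time-to-onset output.

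**What to change.** Before SAP2 is issued, which SAP section 4.0 places ahead of database lock, use one definition in both 8.3.1 and 12.6.1:

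- A TEAE is an event with new onset after the first dose, or an event present before the first dose whose grade rises above its pre-first-dose grade, within one stated window after the last dose.
- A record opened only because severity fell is not a TEAE.
- For a worsened event, the start date is the date of worsening. Carrying back the onset of the symptom would place a true TEAE before the first dose.
- State whether a change of attribution to related, with no rise in grade, qualifies. If it does, record this as a departure from protocol 8.2; if not, remove it from both SAP sections.

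Add the derivation to SAP Appendix 4. The cost is SAP wording and a comparison with the baseline grade in the adverse event dataset. That comparison needs split records to be matched to their baseline record. The CRF is not among the documents, so whether it carries a linking identifier should be checked; matching on preferred term within patient is a possible fallback.

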8.3.2 Vital Signs

Vital signs: systolic and diastolic blood pressure, pulse rate, respiratory rate, body temperature, height and weight.

Sponsor: Mirati Therapeutics, Inc.
Protocol no: 0103-020

8.3.3 Clinical Laboratory Assessments

Clinical laboratory parameters to be collected routinely on-study are listed in Table 3 below.

Table 3: Laboratory Safety Parameters

Hematology Panel	Blood Chemistry Panel
Hemoglobin	Alanine aminotransferase (ALT)
Platelet count	Aspartate aminotransferase (AST)
White blood cell count (WBC)	Alkaline phosphatase
Neutrophil count	Lactate dehydrogenase (LDH)
Lymphocyte count	Total bilirubin (if Total bilirubin is $\geq 2 \times \text{ULN}$ and no evidence of Gilbert's syndrome, then fractionate into direct and indirect bilirubin)
Basophil count	Gamma glutamyltransferase Screening, Day 1, and as clinically indicated
Monocyte count	Lipase
Eosinophil count	Amylase
	Creatinine
Coagulation	Blood urea nitrogen (BUN) or urea, depending on local practice
International normalized ratio (INR)	Uric acid
Prothrombin time (PT)	Total protein
Partial thromboplastin time (PTT)	Glucose (non-fasted)
	Albumin
Urinalysis (dip stick)	Calcium
Blood	Sodium
Glucose	Potassium
Protein	Chloride
	Magnesium
Thyroid Function Test	Bicarbonate $[\text{CO}_2]$
Thyroid-stimulating hormone (TSH)	
Free-T3 (if TSH abnormal)	
Free-T4 (if TSH abnormal)	

8.3.4 Electrocardiograms and echocardiograms

12-Lead electrocardiogram (ECG): rhythm, heart rate, PR, QRS, QT, RR and QTcF, the QT interval corrected for heart rate by the Fridericia's formula. Left ventricular ejection fraction (LVEF; %), pericardial effusion and hemodynamic compromise.

8.3.5 Prior and Concomitant Medications

Medications administered to study participants during the on-study period are captured on a log CRF page. Prior medications are defined as any medications with start and stop dates prior to the date of first dose of study drug. Concomitant medications are defined as medications administered to study participants on or after the date of first dose of study drug.

Sponsor: Mirati Therapeutics, Inc.
Protocol no: 0103-020

9.0 Data Handling

9.1 Missing Dates

The following rules will be applied to impute missing start and stop dates in appropriate data types (e.g., adverse events or concomitant medications).

Start Date

If the start date is completely missing (i.e., the day, month, and year are all unknown) the start date will be set to the date of first dose of study medication.

Missing Day Only

- If the month and year of the incomplete date are the same as the month and year of the **first dose date**, then the day of the **first dose date** will be assigned to the missing day.
- If either the year is before the year of the **first dose date** or if both years are the same but the month is before the month of the **first dose date**, then the last day of the month will be assigned to the missing day.
- If either the year is after the year of the **first dose date** or if both years are the same but the month is after the month of the **first dose date**, then the first day of the month will be assigned to the missing day.

Missing Month Only

- The day will be treated as missing and both month and day will be replaced according to the below procedure.

Missing Day and Month

- If the year of the incomplete date is the same as the year of the **first dose date**, then the day and month of the **first dose date** will be assigned to the missing fields.
- If the year of the incomplete date is before the year of the **first dose date**, then January 1 will be assigned to the missing fields.
- If the year of the incomplete date is after the year of the **first dose date**, then January 01 will be assigned to the missing fields.

If the stop date is complete and the imputed start date is after the stop date, then the start date will be imputed using the stop date.

Stop Date

Missing Day Only

- If the month and year of the incomplete date are the same as the month and year of the **last visit date**, then the day of the **last visit date** will be assigned to the missing day.
- If either the year is before the year of the **last visit date** or if both years are the same but the month is before the month of the **last visit date**, then the last day of the month will be assigned to the missing day.
- If either the year is after the year of the **last visit date** or if both years are the same but the month is after the month of the **last visit date**, then the first day of the month will be assigned to the missing day.

Missing Month Only

Sponsor: Mirati Therapeutics, Inc.

Protocol no: 0103-020

- The day will be treated as missing and both month and day will be replaced according to the below procedure.

Missing Day and Month

- If the year of the incomplete date is the same as the year of the **last visit date**, then the day and month of the **last visit date** will be assigned to the missing fields.
- If the year of the incomplete date is before the year of the **last visit date**, then January 1 will be assigned to the missing fields.
- If the year of the incomplete date is after the year of the **last visit date**, then January 01 will be assigned to the missing fields.

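### A stop date known only by year is set to 1 January when that year precedes the last-visit year, so stops can precede starts and some continuing medications can be tabulated as prior

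*SAP*

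**What the plan says.** SAP Section 9.1 gives imputation rules for incomplete start and stop dates, naming adverse events and concomitant medications as examples. For a stop date with day and month missing there are three branches:

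- Stop year equal to the last-visit year ("If the year of the incomplete date is the same as the year of the last visit date"): the day and month of the last visit are used.
- Stop year before the last-visit year: "then January 1 will be assigned to the missing fields".
- Stop year after the last-visit year: 1 January again.

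A stop date lacking only its month follows the same rule: "The day will be treated as missing and both month and day will be replaced according to the below procedure".

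If only the day is missing and the month is before that of the last visit, "then the last day of the month will be assigned to the missing day".

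The one consistency check in the section sits in the start-date block. It applies only when the stop date is fully recorded, and it pulls a later imputed start back to that stop.

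Section 8.3.5 then classifies medications by date. "Prior medications are defined as any medications with start and stop dates prior to the date of first dose of study drug". Anything taken from the day of first dose onward counts as concomitant. Section 12.3.2 tabulates the two groups separately.

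**The concern.** For stop dates, the day-only rule for earlier months and the same-year rule both lean late: month end in one case, the last visit in the other. The earlier-year branch leans as early as it can, and the SAP gives no reason. The existing check requires a complete stop date and moves the start, so it never examines an imputed stop.

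Two outputs are at stake. Listings can show an adverse event or medication that ends before it begins. The prior and concomitant medication tables can also place a drug that the patient was taking on treatment among the prior medications, understating concomitant use.

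**Working it through.** The SAP states no figure for this rule, so there is none to reproduce. The check applies the rules of Sections 9.1 and 8.3.5 to patient dates. Those dates are assumed for illustration, because the documents contain none.

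**Rule.** Let *y* be the recorded stop year, with day and month missing, and *L* the last-visit date.
- If *y* = year(*L*), imputed stop = *L*.
- If *y* < year(*L*), imputed stop = 1 January *y*.
- A medication is prior if start < first dose and stop < first dose.

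**Size of the error in the earlier-year branch.** The true stop lies between 1 January and 31 December of *y*. The imputed stop is therefore 0 to 364 days too early, or 365 in a leap year, and never too late.

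**One adverse event.** First dose 15 June 2016, last visit 15 March 2017, onset 10 September 2016, stop recorded as 2016. Since 2016 < 2017, the imputed stop is 1 January 2016. Onset is day 254 of 2016 and the stop is day 1, so the stop precedes onset by 254 − 1 = 253 days.

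**All possible dates.** Adverse-event onsets run from first dose to year end (or the last visit, if sooner). Medications start on any of the 365 days before first dose and truly stop on or after first dose in the same calendar year. The stop is recorded by year only.

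| First dose | Last visit | AE stop before start | Continuing medication classed as prior | Of those pairs, imputed stop also before start |
|---|---|---|---|---|
| 15 Jun 2016 | 15 Mar 2017 | 200/200 | 73,000/73,000 | 33,000 (45.2%) |
| 1 Nov 2016 | 15 Mar 2017 | 61/61 | 22,265/22,265 | 18,544 (83.3%) |
| 1 Feb 2016 | 1 Feb 2018 | 335/335 | 122,275/122,275 | 10,050 (8.2%) |
| 15 Jun 2016 | 20 Dec 2016 | 0/189 | 0/68,985 | 0 |

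The pair counts are 365 start days times the eligible stop days, for example 365 × 200 = 73,000. The last row is the same-year branch, where neither fault appears.

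In the first three rows, 17% to 92% of the misclassified medications show no date inversion (100 − 83.3 and 100 − 8.2). A check for inverted dates would therefore not find them. Where such a check did fire, moving the stop to the start would leave it before first dose, so the drug would still be prior.

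**Same scenarios with 31 December in the earlier-year branch.** Adverse-event inversions are 0 and continuing medications classed as prior are 0 in all four. The opposite error appears for medications that truly stopped before first dose in the first-dose year. All possible stop days then count as concomitant: 166/166, 305/305 and 31/31 in the three cross-year scenarios. The existing same-year branch already does this (166/166 in the fourth scenario).

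**The case against.** A reader might infer more than the text supports.

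- **That every year-only stop date goes to 1 January.** It does not. The same-year branch uses the last visit. The fault needs a stop year before the last-visit year, so follow-up must cross a calendar year.
- **That any on-study medication can become prior.** A drug started on or after first dose fails the start condition in Section 8.3.5. Only drugs begun before first dose and stopped in the first-dose calendar year are exposed.
- **That adverse-event results change.** Sections 12.6.1 and 12.6.2 count patients and specify no duration or time-to-resolution summary. Treatment-emergent status rests on onset or worsening. Some DLT exclusions use durations, but nothing in the SAP derives DLT status from imputed dates.
- **That the wording was copied from the start-date rule.** The bullets match, but the documents do not say how they arose.

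Three defences have some force. First, Section 8.3.5 does not say that its definitions use imputed dates or are mutually exclusive, so loss from the concomitant table is a consequence of programming from dates rather than a stated rule. Even so, Section 9.1 imputes these dates, and no other basis for classification is given. Second, Section 11.0 provides data screening and output review before lock. It names no stop-before-start check, and the misclassified records without inversion would look normal. Third, choosing 31 December over 1 January exchanges one misclassification for another. That is true for medications and is a cost of the fix. It does not excuse impossible dates, and it leaves the earlier-year branch at odds with the SAP's other stop-date rules.

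**Conclusion.** The rule is wrong as written for stop dates lacking day and month, or month alone, whose year precedes the last-visit year. In the cross-year scenarios examined, every adverse event starting on treatment and ending in the first-dose year received a stop before its start. Every medication begun before first dose and continued into treatment within that calendar year was classed as prior.

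This is a minor point. It touches listed stop dates and the prior and concomitant medication tables only. The number of affected records cannot be known from the documents and is probably small, since it requires a stop month that was never recorded. The percentages describe what the rule does to an affected record, not how often such records occur. They rest on the assumed patient dates and on classification being programmed from imputed dates.

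**What to change.** In SAP Section 9.1, stop dates, day and month missing: when the year is before the last-visit year, assign 31 December of the recorded year. No cap at the last visit is needed, because that date always precedes a visit in a later year. Add a second line stating that an imputed stop date may not precede the start date and, if it would, is set to the start date. This check also covers other branches, such as an event that begins after the last visit.

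The cost is one changed line, one added check and a macro edit. The SAP Introduction already provides a change log and a final version before database lock. State the trade-off in the SAP: a medication truly stopped before first dose in the first-dose year, with month unknown, will be tabulated as concomitant, as the same-year branch already does.
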